8.3 Setting

8.3.1 Vaccination Sites

Vaccination sites will include various site types such as general/primary care practices, hospitals, vaccination centres, mobile vaccination units, and long-term care facilities. The types of sites may differ over time and between countries, reflecting differences in local practices and vaccination policies. To boost enrolment of older adults (≥ 65 years of age), the choice of vaccination sites for the study will target locations likely to administer vaccines to older adults and geographical areas with higher populations of older adults. The study will initially include vaccination sites in Germany, France, Spain, and Sweden, but the study may be expanded to additional EU countries.

8.3.2 Study Population

8.3.2.1 Eligibility Criteria

Participants are eligible to be included in the study only if all the following criteria apply:

- Aged 18 or older at the time of vaccination.
- Received AZD1222 as the first dose of COVID-19 vaccination in the prior 28 days.
- The participant has provided sufficient details to validate the vaccination (vaccination card, batch/lot number, and/or regional vaccination register details).
- Provided informed consent to participate in the study, either personally or through a legal representative.
- Able and willing to provide responses to study notifications using the mobile device app, web portal, or call centre or have a proxy (a caregiver, family member, or other trusted individual) who can do so on their behalf.
- Able and willing to grant, personally or through a legal representative, permission to contact the participant's healthcare providers and to access the participant's medical records at the time of vaccination and during the post-vaccination follow-up period.

8.3.2.2 Key Subpopulations

This real-world, non-interventional study will enrol all eligible participants but, in particular, will seek to enrol older adults, with a target of 50% of participants aged \geq 65 years. The study will also aim to have equal enrolment of male and female participants. Additional subpopulations of interest in this study include:

- Pregnant women, breastfeeding women
- Immunocompromised participants

SCI

- Participants with autoimmune or inflammatory disorders
- Frail participants with comorbidities (eg, chronic obstructive pulmonary disease, diabetes, chronic neurological disease, cardiovascular disorders)

8.3.3 Participant Withdrawal and Lost to Follow-up

A participant may withdraw from the study at any time at his/her own request or may be withdrawn at any time at the discretion of the investigator for safety, behavioural, compliance, or administrative reasons. If the participant withdraws consent for disclosure of future information, the Sponsor may retain and continue to use any data collected before such a withdrawal of consent. Participants who choose to withdraw will be asked for the reason they are leaving the study.

A participant will be considered lost to follow-up if he or she fails to respond to the study notifications and does not respond to subsequent follow-up attempts. At least 2 follow-up attempts will be made, at least one week apart.

For participants who are apparently lost to follow-up, study personnel will attempt to collect the vital status of the participant within legal and ethical boundaries for all participants enrolled. Participant's emergency contact, provided at enrolment, will be contacted and asked for the status of the participant, and, if appropriate, the reason the participant has not responded to study notifications. Public sources may be searched for vital status information. If vital status is determined as deceased, this will be documented, and the participant will not be considered lost to follow-up. Sponsor personnel will not be involved in any attempts to collect vital status information.

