8.2 Study Design

This is a Phase IV real-world, observational, non-interventional, prospective cohort study of adults who receive the AZD1222 vaccine. Vaccine recipients \geq 18 years old will be recruited

for the study at vaccination sites in Germany, France, Spain, and Sweden. Awareness of the study may be raised through social media and traditional media (television, print, and radio).

In this study, vaccination sites will not act as traditional study investigators and will not be responsible for participant screening or safety follow-up. Rather, participants will self-enrol in the study using the study app, web portal, or call centre and will submit answers to study questionnaires using those methods. Event follow-up and assessment, where needed, will also be performed remotely by study personnel. The digital platform will also include an investigator dashboard where investigators and selected study personnel can view and track, in real time, all adverse events (AEs) submitted. Role-based permissions will ensure only authorised personnel can view identifying confidential data like participant names.

Participants will enrol in the study after vaccination with AZD1222. Enrolment is permitted within 28 days of the first dose of AZD1222 and can be completed at the vaccination site or remotely. If a vaccine recipient chooses to enrol in the study at the vaccination site, a study research coordinator may be present and can assist by:

• Providing information about the study.

SCI

- Explaining the study participation options: study app, web portal, or telephone communication with the call centre.
- Assisting the participant with the informed consent process.
- Checking if participants meet the eligibility criteria and providing vaccination details.
- Recording contact information for the participant, the emergency contact (in case of apparent loss to follow-up), and the participant's proxy, if needed.
- Providing the proxy with instructions on how to assist the participant with reporting.

For vaccine recipients who would prefer to enrol remotely at a later date, up to 28 days after the first vaccine dose, a study information brochure will be available that includes instructions to remotely enrol (including electronic informed consent completion, where permitted) and their vaccination details (if a vaccination card was not already provided).

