Primary and secondary analyses. The primary analysis will only include participants who enrolled within 7 days of vaccination with the first dose of AZD1222. All AEs collected, regardless of seriousness, will be tabulated. The cumulative incidence of SAEs, AESIs, and medically-attended AEFIs will be computed as the proportion of participants who reported an event among all AZD1222 vaccinated participants who completed each study-defined follow-up interval as well as among all AZD1222-vaccinated participants regardless of completion status, in combination with corresponding patient-years.

Where feasible, incidence rates will be calculated (in person-years), both by dividing by number of person-years, as well as by taking into account death as a competing event and withdrawal from the study/loss-to-follow-up as a censoring event (using cumulative incidence). Kaplan-Meier curves will be used for this analysis where appropriate.

Summaries of SAEs, AESIs, and medically-attended AEFIs by intensity, seriousness, and relatedness will also be presented.

In the pregnancy sub-cohort, the prevalence of pregnancies that resulted in live births, spontaneous abortions, and stillbirths will be summarised along with any other pregnancy outcomes reported within the AESI medical concept of Pregnancy Outcomes - Maternal. Infant outcome measures will also by summarised by the prevalence of events in the AESI medical concept of Pregnancy Outcomes – Neonates, including small for gestational age and major congenital malformations.

Additional Supportive Analysis. To support safety signal evaluation, a risk assessment will be conducted for AESIs using background event rates established through the ACCESS project or another source (Meurs and Kant 2020, ACCESS 2020). To further enhance background rate identification, additional literature review will be conducted if ACCESS data is insufficient or unavailable. Appropriate risk windows will be estimated for these analyses

and counts of AESIs that occurred within the prespecified risk window will be compared against expected values using sequential testing. Where appropriate, analyses will be stratified by sex and age. To assess whether larger risks can be found based on bias, the background rates based on the external sources will be evaluated as they are and with additional scenarios.

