Subgroup Analyses. Incidence rates and potential differences in the risk and pattern of participants experiencing AEs within different subgroups will be explored, including categories that are considered missing information at the start of the study. The subgroup analyses will include:

- Age at vaccination (18 to 34, 35 to 49, 50 to 64, 65 to 79, and \geq 80 years)
- Sex (male, female)
- Race/ethnicity
- Country (Germany, France, Spain, Sweden)
- Previous COVID-19 infection
- Pregnant/breastfeeding women
- Participants with immunodeficiency
- Participants with autoimmune or inflammatory disorders
- Frail participants with comorbidities (chronic obstructive pulmonary disease, diabetes, chronic neurological disease, or cardiovascular disorders)
- Participants who receive other vaccines in addition to AZD1222 (within 1 month)
- Number of AZD1222 doses received (1 dose, 2 doses)

Handling of Missing Data. No restrictions on the percentage of missingness will be made, but the baseline characteristics of the participants lost-to-follow-up will be tabulated. The differences between the baseline characteristics for the total group and the group lost-to-follow-up will be related to the subgroup analyses to assess for a possible impact on AE risk. Adjustment for missingness will be further specified in the statistical analysis plan but may include multiple imputation, joint modelling, and inverse probability weighting.

To deal with missingness due to death, death will be interpreted as a competing risk in the above analyses.

Mitigation of Potential Bias and Confounding. Strategies include:

- To account for possible sampling bias due to the recruitment of vulnerable populations first (residual confounding), in the risk assessment analyses, in addition to the expected background event rate, the rates will be multiplied by 1.2, 1.5, and 2.0 times, for example.
- Subgroup analyses within risk assessment analyses will also be performed, if feasible. When characteristics are found that both are related to differences in AE risk and to differences between study participants and the overall vaccinated population, weighting will be added.
- Additional sensitivity analyses will include:

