Recall bias	This study will permit enrolment remotely up to 28 days after the first vaccine dose and will only periodically remind participants to report outcomes, introducing the possibility of recall bias.	 The following study elements address recall bias: The primary analysis will be limited to participants who enrolled within 7 days of their first vaccine dose. Participants must complete the scheduled questionnaires within certain time windows.
Misclassification of events	Participants could self-report events inaccurately.	Study personnel will follow up to confirm as many event details as possible using medical records, as described in Section 10.2.

Table 4Study Limitations and Mitigations

Potential limitation	Reason for potential limitation	Rationale or mitigation
Failure to report events due to incapacity	Primary method of reporting outcomes is self-reporting	All participants will be asked to provide an emergency contact when they enrol. As described in Section 8.3.3, if a participant seems lost-to-follow-up, study personnel will reach out to the emergency contact and/or perform a search for vital status information.
Data analysis limitat	ions	
Generalisability	Point estimates and confidence intervals resulting from the analyses should only be interpreted as indications and not as reflective of a 'true' underlying estimand because of the limitations of conducting a study during an ongoing pandemic. This may impact the interpretation of the results as well as the ability to generalise the results to post-pandemic circumstances.	Will be considered for final analysis.
Missing data	Loss of participants in follow-up and/or missing data are limitations inherent in all primary data collection observational studies. In this non-interventional, observational study, participants may not respond to all prompts and may not complete the full 18-month follow-up period.	See Section 8.8 for planned handling of missing values in the analyses.

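### Section 8.3.3 lets investigators withdraw participants for safety or compliance reasons in a non-interventional safety study, with no provision for continued follow-up or a recorded reason

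*Protocol*

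**What the plan says.** Section 8.3.3 allows two kinds of exit by decision. Participants may leave at their own request, or a participant "may be withdrawn at any time at the discretion of the investigator for safety, behavioural, compliance, or administrative reasons". None of the four grounds is defined. The section asks for a reason only from participants who themselves choose to leave. It also says that "the Sponsor may retain and continue to use any data collected before such a withdrawal of consent", a sentence written for withdrawal of consent and not for a withdrawal decided by the investigator. Emergency-contact and vital-status tracing is described for participants who appear lost to follow-up.

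On the nature of the study, section 8.2 calls it non-interventional and states: "Participants will enrol in the study after vaccination with AZD1222". Section 10.2 sets adverse event collection to run from consent to 18 months after the first dose.

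Section 8.8 plans several estimates:
- a cumulative incidence computed as the proportion of "participants who reported an event among all AZD1222 vaccinated participants who completed each study-defined follow-up interval";
- the same proportion among all vaccinated participants whether or not they completed, reported with patient-years;
- where feasible, incidence rates, and a cumulative incidence with death as a competing event and "withdrawal from the study/loss-to-follow-up as a censoring event".

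Neither proportion is named as the main one. On missing data, section 8.8 says "No restrictions on the percentage of missingness will be made", and Table 4 in section 8.10 expects that "participants may not respond to all prompts and may not complete the full 18-month follow-up period".

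**The concern.** In a trial that gives treatment, withdrawing someone for safety can protect them from further exposure. Here participation means answering questionnaires and allowing access to medical records. Withdrawal for safety protects nobody from a study treatment. It stops data collection in a study whose purpose is to collect safety data.

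The compliance ground fits no better. The missing-data plan accepts any amount of missingness, and the limitations table expects unanswered prompts. A compliance withdrawal would remove the partial responders whom those passages keep.

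The statistical issue is exit that depends on the outcome. If the reason for leaving is an event, the people who remain are no longer representative of those who started. Events that are never collected cannot be restored in the analysis. This matters most for the 18-month secondary objective and for long-term safety, which section 6.2 lists as missing information.

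**Working it through.** **1. The plan's own precision figure.** Section 8.8 gives a maximal confidence interval of ±0.8% for 15,000 participants. At a proportion of 50%, 1.96 × √(0.5 × 0.5 / 15,000) = 0.80%. The figure reproduces and does not depend on the withdrawal rule.

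**2. What each estimate loses.** Take a participant with a non-serious AESI in Week 2 whom the investigator withdraws in Week 5. Contacts fall at Weeks 1, 4, 8 and 14.
- *Completer proportion.* If the participant answered at Week 4, the event counts for the interval ending then. The participant does not complete to Week 14, so person and event both leave that proportion.
- *All-vaccinated proportion.* The AESI stays in the numerator, provided that data collected before an investigator withdrawal are kept. The two denominators imply this, but section 8.3.3 does not state it. A later SAE is not seen, while the person stays in the denominator.
- *Time-based analysis.* The AESI comes before the censoring, so it counts. For the SAE curve the participant is censored because of an event. If such participants have a higher later risk than those who remain, the censoring is informative.

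**3. Size in the completer proportion.** Inputs: N = 15,000 from section 8.8. The true risk p, and the share w of participants with events who are withdrawn before completing the interval, are assumptions, because the protocol gives neither. No other dropout is assumed.

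Events among completers = Np(1 − w). Completers = N − Npw. The estimate is therefore p(1 − w) / (1 − pw).

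| p | w | Calculation | Completer estimate | Relative loss |
|---|---|---|---|---|
| 1% | 5% | (150 − 7.5) / (15,000 − 7.5) | 0.95% | 5% |
| 1% | 20% | (150 − 30) / (15,000 − 30) | 0.80% | 20% |
| 30% | 20% | 0.24 / 0.94 | 25.5% | 15% |

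The relative loss equals w(1 − p) / (1 − pw). It is close to w only when events are uncommon.

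**4. Against sampling error.** At p = 1% and N = 15,000 the 95% half-width is 1.96 × √(0.01 × 0.99 / 15,000) = 0.16 percentage points. The bias at w = 20% is 0.20 points. This comparison changes with the inputs:
- The primary analysis takes only participants enrolled within 7 days of the first dose, so its N is smaller. At an illustrative N = 7,500 the half-width is 0.225 points, larger than the bias.
- At p = 0.1%, w = 20% and N = 15,000, the bias is 0.02 points against a half-width of 0.05.

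**5. Whether the effect could be seen.** Section 8.8 tabulates study withdrawal but does not separate the participant's decision from the investigator's. The baseline comparison planned under missing data covers only participants lost to follow-up. With no recorded reason, event-related withdrawals could not be identified from what the protocol requires.

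**The case against.** A reader might infer that the rule removes exactly those who had events, and that it removes those events from the primary estimate. The documents support neither reading. The clause is permissive, *safety* is undefined, and behavioural, compliance or administrative reasons need not follow an event. The completer proportion is only one of two reported proportions. The other covers all vaccinated participants regardless of completion and keeps events already recorded. Intervals completed before the withdrawal still count, and an event before censoring still counts in the time-based analysis.

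There is more on the same side. Section 10.2 has reported events flagged, confirmed and followed up with the healthcare provider, and nothing says that an event triggers withdrawal. Persistent non-response is classed as loss to follow-up after at least two further attempts, and no passage makes skipped prompts a reason for withdrawal. Withdrawals are tabulated. Adjustment for missingness is left to the SAP, which is not at hand, and the options named include joint modelling, which goes beyond adjustment for baseline variables.

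These points limit the likely harm, but they do not give the safety and compliance grounds a purpose in this study. Who may be withdrawn, and whether follow-up then continues, is for the protocol to settle. Modelling of informative exit is also weaker when the reason for exit is not recorded.

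**Conclusion.** The point holds as a cheap improvement to a stated rule. Section 8.3.3 permits exit that can depend on the outcome, and the protocol neither provides for follow-up afterwards nor requires the investigator's reason. Where such a withdrawal follows an event, the completer proportion is biased downward for intervals not completed, the censoring becomes informative, and later events are lost from all estimates.

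The size cannot be derived from the documents. The fall from 1% to 0.95% or 0.80% rests on assumed withdrawal shares of 5% and 20% among participants with events. A general statement that the bias exceeds sampling error, or that the relative loss is the same at any event frequency, would not hold, as steps 3 and 4 of the working show.

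**What to change.** In section 8.3.3:
- Delete safety and compliance as grounds for investigator withdrawal.
- State that participants with an adverse event or missed questionnaires stay in follow-up until Month 18, death, their own withdrawal, or loss to follow-up as that section already defines it.
- For any remaining investigator withdrawal, administrative or behavioural, require that the reason be recorded and that data already collected be kept. Medical-record and vital-status follow-up should continue where consent allows. The eligibility criteria already require permission to contact healthcare providers and use medical records.

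This takes a few sentences. It leaves the participant's right to withdraw untouched and does not bar behavioural discretion. The cost is that some poorly responding participants stay on the contact list, with record and vital-status tracing for the few whom investigators still withdraw.

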8.4 Variables

8.4.1 Study Variables to be Collected

Table 3 summarises the data collection plan.

CCI

Table 3Data Collection Plan for Key Variables and Information

	Enrolment (post-	Post-vaccination follow-up with participants via app, email, or phone call (months, weeks after first vaccine dose)											
Procedure or variable	vaccine dose 1) ^b	1 wk	4 wk	8 wk	14 wk	4.5 m 20 wk	6 m 26 wk	9 m 39 wk	12 m 52 wk	15 m 65 wk	18 m 78 wk	Data source(s)	Data capture format
					Conse	nt and C	ontact Det	ails					
Informed consent ^a	Х											Participant	ICF form
Choice of digital or non-digital participation	Х												
Personal contact information, including emergency contact	Х											Participant	Profile questionnaire
Primary HCP and contact information	Х												
Name and contact information for proxy, if needed	Х											Participant	App or web portal interface
					v	accinatio	n Details						
Vaccine product (brand)	Х		Star	rting at W	aalz 1							Vaccination site, RC, participant	Vaccination details questionnaire
Vaccination date	Х		particij	pants can	complete								
Vaccine batch/lot number	Х			ost-vaccin									
Type of vaccination site	Х			nd dose. S									
Photo of vaccination card ^c	Х			es are exp								Participant	Vaccine card photo
Any antipyretic/pain-reliever within 5 days of vaccination		Х	X between Week 4 and Week 14 based on recommended schedules.									Participant	Antipyretic/ pain-reliever questionnaire
			 ]	Participan	t Backgr	ound Info	rmation					
Age	Х												
Sex/gender	Х											1	
Height/weight	Х											-	
Race/ethnicity d	Х											Participant	Background questionnaire
Country of birth/residence	Х							questionnune					
Employment status	Х												
Smoking status/history	Х												

CCI

Table 3Data Collection Plan for Key Variables and Information

	Enrolment (post-	Post-vaccination follow-up with participants via app, email, or phone call (months, weeks after first vaccine dose)											
Procedure or variable	vaccine dose 1) ^b	1 wk	4 wk	8 wk	14 wk	4.5 m 20 wk	6 m 26 wk	9 m 39 wk	12 m 52 wk	15 m 65 wk	18 m 78 wk	Data source(s)	Data capture format
						Medical l	History						
Prior infection with SARS- CoV2 or prior COVID-19 disease, including symptoms	Х											Participant,	
Recent non-AZD1222 vaccination	х	Х	Х	Х	X		Х	Х	X		Х	medical records	Medical history questionnaire
Select comorbidities and medications ^e	X												
		•	•			Safety Ou	itcomes						
 SAEs, AESIs, and medically attended AEFIs ^f Symptoms Diagnosis Onset date/duration Intensity Resolution Treatment Seriousness ^g Causality ^g 		X	х	X	X		Х	X	X		X	Participant, HCP, medical records	Health status questionnaire, AESI form (when applicable)
		Х	х	Х	X		Х	X	x		X	Participant, medical records	CCI
Death												Emergency contact, proxy, HCP, medical records	Safety database

Table 3Data Collection Plan for Key Variables and Information

	Enrolment (post-		Post-vaccination follow-up with participants via app, email, or phone call (months, weeks after first vaccine dose)										
Procedure or variable	vaccine dose 1) ^b	1 wk	4 wk	8 wk	14 wk	4.5 m 20 wk	6 m 26 wk	9 m 39 wk	12 m 52 wk	15 m 65 wk	18 m 78 wk	Data source(s)	Data capture format
		Pro	egnancy	Status an	d Outcom	es (Pregr	ant and B	reastfeedi	ng Wome	n Only)			
Pregnancy status, including maternal medical and obstetric history	X	Х	Х	Х	Х		Х	х	X		X	Participant, medical records	Pregnancy status questionnaire
Pregnancy/infant outcomes, pregnant participants			articipants who report pregnancy at the time of vaccination will be followed-up at 12 months after their estimated last menstrual period and, for those reporting live-birth, at infant age up to 12 months to assess pregnancy/infant outcomes. ^j						Participant, medical records	Pregnancy follow- up questionnaire			
Breastfeeding status, including infant outcomes	X	X	X	Х	Х		Х	Х	Х			Participant, medical records	Breastfeeding status questionnaire
Parent/caregiver informed consent ⁱ	Х											Participant	Parent/caregiver ICF
	Patient-reported Quality of Life Outcomes									·			
CCI	X ^k					X ^k				X ^k		Participant	CCI
CCI						X ^k				X^k		Participant	CCI

^a Informed consent will include consent to participate in the study as well as to contact HCPs and for the release of medical records relevant to the study.

^b Participants can enrol up to 28 days after their first vaccine dose.

^c For digital participants only. For non-digital participants, vaccination details will be validated by the call centre.

^d Will be collected in countries where permitted.

^e Selected medical conditions: neuroimmune condition, other neurological condition, bleeding disorder, asthma, chronic obstructive pulmonary disease, diabetes, cerebrovascular conditions, heart disease, other cardiovascular disease, chronic kidney disease cancer, autoimmune disease, solid organ transplant recipient, other condition affecting immune system, liver disease, history of allergic conditions, depression/anxiety, viral/bacterial infection leading to hospital admission, and other chronic condition or conditions for which participant received treatment or medication in last month. If a participant indicates having any of these conditions, the participant will be asked if they are currently taking any medication or being treated for it. Specific medication will not be asked unless the participant indicates they are taking an immunosuppressant.

^f Adverse event reports can be scheduled (timed follow-ups) or unscheduled. At the scheduled timepoints, participants will be asked if they've had any new or worsening health issue resulting in consultation with a medical doctor, an emergency room visit or hospitalisation, or a significant or long-term disability or incapacitation. When a participant responds "yes", the participant will be asked for more details. For reported COVID-19 cases, this will include patient-reported symptoms.

^g Healthcare providers will provide input and study personnel will assess the seriousness and causality of AEs.

h

CC

PASS Protocol AZD1222, D8111R00003

CI

- ⁱ Participants vaccinated with AZD1222 during pregnancy or up to 45 days before the estimated date of conception will be asked to follow outcomes in their child for up to 12 months after birth. Breastfeeding participants will also be asked to follow-up on their child's health. Before any request for a child's medical records, the participant will be asked for additional informed consent. The child's other parent may also be asked for consent, depending on local requirements.
- ^j Outcomes in infants will be requested up to 12 months of age. However, follow-up of pregnancy and infant outcomes will not be continued past 24 months post-first dose for the last participant enrolled in the study.

k CC

As a data source, participant means either the participant directly or the participant's designated proxy.

For the safety outcome follow-ups at Weeks 1, 4, 8, 14, and Month 6, 9, 12, and 18, depending on the interval between scheduled contacts, participants will receive reminders for 2 to 8 weeks after the initial notification to complete the questionnaire.

AE, adverse event; AEFI, adverse event following immunisation; AESI, adverse event of special interest; CSP, clinical study protocol; HCP, healthcare provider, CC

; ICF, informed consent form; m, month; NA, not applicable; CCI

; RC research coordinator; SAE serious adverse event; wk, week.

